2.3 Inclusion/Exclusion Criteria

A total of 230 full-term (>37wks gestational age) newborn infants exposed to opioids *in utero* will be studied over the five-year funding period: 100 at UMass and 130 at UPitt.

2.3.1. Inclusion Criteria. Infant inclusion criteria include documented opioid drug exposure (i.e., positive toxicology screen; exposure questionnaire and medical record history) and comprise the general population (Worcester, MA and Pittsburgh, PA demographics) without restriction in regard to gender, race or socioeconomic status. Infants may also have additional prenatal poly-drug exposure (e.g., benzodiazepines, barbiturates, amphetamines, cannabinoids, alcohol, nicotine and/or caffeine). Inclusion of pregnant women is for the sole purpose of obtaining consent to study the infant post-delivery, and to review infant and maternal medical records. Pregnant women are included because we will be recruiting pregnant women who are at risk for delivering infants with NAS due to drug exposure in utero. Prenatal consents are needed to help expedite feasibility of study of infants soon after delivery. Infants will not be studied in utero, but will only be studied after delivery.

2.3.2. Exclusion Criteria. Subjects with clinically significant fetal anomaly, congenital abnormality, adverse pregnancy outcome, hydrocephalus or intraventricular hemorrhage >grade 2, seizure disorder not related to drug withdrawal, clinically significant cardiac shunt, anemia (hemoglobin<8g/dL), requires mechanical respiratory support or is being treated for MRSA or infection at the time of the study will be excluded, or other medical condition aside from NAS will be excluded. Informed consent will be obtained from parent(s) or legal guardian of all participants.

2.4 Sample Size and Power Calculations

For all Aims there is sufficient sample size to detect clinically meaningful differences with 90% power, described below:

2.4.1. Specific Aim 1. We use the Finnegan NAS score as the primary outcome for this aim. From Nayeri et al. [70] and our own pilot data, the Finnegan NAS score in opioid-exposed infants had a SD of 2.0-2.5. Assuming a standard t-test with a two-sided alpha level of 0.05 for the unadjusted comparison of the Finnegan scores at a particular time point with the more conservative standard deviation (SD.=2.5), the sample size of 115/group can detect a difference of 1.1 with 90% power. Taking into account the repeated measures of the Finnegan NAS score, assuming intra-infant correlations of 0.5-0.7, we will have 90% power to detect a difference of 0.80-0.95 in a mixed effects model for the overall (i.e., across time) treatment group coefficient. With a mixed effects model, we will also add covariates as described above to determine an adjusted treatment effect. We expect that this model may have even more power than described here due to the partitioning of the overall variance among the covariates. Because infants are hospitalized and under observation until release, we expect only minimal attrition and loss of information.

2.4.2. Specific Aim 2. We use Movement as primary outcome for this aim. Based on our preliminary data in 26 NAS infants (OFF: mean movement 40% of condition time, SD=10%; ON: mean movement 26% of condition time, SD=9%) and

assuming a two-sided paired t-test at alpha=0.05 for the unadjusted treatment effect, we estimate 25 infants per group will give us 90% power to detect a reduction of 7% in movement between the two treatment groups (a relative reduction of about 20% from 40% in OFF to 33% in ON) with a conservative SD of 10% (from the pilot study).

2.4.3. Specific Aim 3. We use Bayley-III as primary outcome for this aim. We anticipate an attrition rate of ~40% in the 1-year follow-up assessments. Assuming a sample size of 60 children/group at 1 year with a two-sided standard t-test at alpha=0.05 and a SD of 14 for the Bayley-III cognitive composite scale, [71] we will have 90% power to detect a difference of 8.5 (or about a 12% difference) between the two groups at 1 year of age. The other Bayley scales have similar SDs, so the results will be similar. For a longitudinal analysis of the Bayley-III cognitive composite scale over the follow-up visits (1, 3, and 12 months of age), we will use a mixed effects model as above with months of age as the time metric in the model. Assuming the same sample size with intra-child correlations of 0.5-0.7 for a mixed effects model with a two-sided test for the treatment group coefficient at alpha=0.05, we will have 90% power to detect a treatment effect of 6.8-7.4 (depending on the correlation) using the treatment group coefficient. We can also add covariates to this model to estimate an adjusted treatment effect.

Each child will be classified as impaired or not based on the results of the battery of tests given over one year.[69] Assuming a worse-case scenario (in terms of SD of a proportion) of 50% impairment in the SCC group, with 60 children/group we will have 90% power to detect an unadjusted absolute improvement of 28% (50% vs. 78%) or a relative improvement of 56% in the SVS group with a z-test with a two-sided alpha =0.05. For an adjusted estimate of the improvement in percent impairment at one year, we will use a logistic model with other covariates added. For a longitudinal assessment of impairment, we will use a GEE longitudinal logistic model with the same approach for model building as above.

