3) Movement Activity. Movement periods will be assessed via actigraphy, a simple non-invasive measurement using a wireless, lightweight sensor worn around the infant's limb (Respironics[®]). The sensor is ~1.5"x1" and held in place with a soft foam tapeless wrap (Posey[®]). Actigraph sensors applied to the infant's limb will continuously record the frequency of movements throughout the duration of the infant's hospitalization, starting within 24-48 hrs post birth. This will allow measurement of frequency of leg movements (index of irritability, sleep fragmentation, wake and quiescence (index sleep) throughout hospitalization).^[46, 47] Data will be recorded in 1-min epochs to evaluate for movement frequency (index of activity) and quiescence over 12h and 24h intervals and/or during periods when infants are documented in the crib (mattress on or off). Digitized signals will be stored on electronic data base. Data will be analyzed via computerized programs, stored in excel spreadsheets, and entered by a research investigator via secure password protected computer into REDCap database.

4.1.2. Specific Aim 2. Examine physiological responses to SVS compared to SCC at two stages of withdrawal severity – Standard Measurements and Recording.

Changes and relationships among physiological signals will be quantified in a sub-population of study infants at UMass. For each session, physiological signals will be recorded continuously for ~6-8 hrs using proprietary acquisition system. Respiratory inductance plethysmography will be used to measure infant's breathing (Somonstar[®]); infant's abdominal muscle movement will provide detection of interbreath intervals (index of respiratory stability) and respiratory rate. Electrodes over the skin surface of the chest will be used to record electrocardiographic activity (ECG; Embla[®]) to allow for detection of cardiac R-R intervals (index of interbeat variance and heart rate). A probe attached to the infant's foot will measure arterial-blood oxygen concentration (Masimo[®]). Quality of the plethysmographic activity characterized in the pulse signal will also allow for identification of movement period duration. Movement frequency will be assessed with actigraphy using a wireless sensor worn around the infant's limb (Respironics[®]).

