4.3.3. Specific Aim 2: Study design allows systematic quantification of condition effects on breathing (IBI variance and respiratory rate), cardiac rhythm (R-R variance and heart rate), movement activity (frequency and duration), blood oxygenation (durations<85%), and skin temperature. Histogram of frequency-bands of cardio, respiratory and movement incidents will be determined. As with Aim 1, mixed effects models will be used to examine if SVS, within infants and between SVS and SCC infants: 1) Decreases irritability and sleep disruption/fragmentation indexed by movement frequency and duration; 2) Improves cardio-respiratory control: reduces bradycardia/bradypnea. tachycardia/tachypnea and increases incidents of eucardia/eupnea; and 3) Reduces other NAS symptoms: e.g., temperature; oxygenation. Additional computational signal analysis. We have developed novel statistical point process algorithms that measure cardio-respiratory dynamics and movement over continuous time domains.^[67, 68]The variable characteristics of respiratory (IBI) and cardiac (RR) signals are integrated with the dynamic characteristics of these signals to provide instantaneous, moving estimate of mean, variance and other dynamic measures (e.g., spectrum, poles, frequency).^[68] These measures will be used to examine temporal dynamics of respiratory and heart rate rhythm, and explore corresponding physiological relationships with movement over time; e.g., Do IBI changes that reflect caudal brainstem function precede cortical behaviors such as arousal (e.g., movement)? Time series of movement periods will be analyzed using Wavelet derived SAP throughout stimulation ON and OFF to evaluate temporal dynamics including: 1) Response time for improvement in rhythm relative to the onset of stimulation; 2) Whether there is loss of efficacy over time (during each 30 min stimulus period as well as from one period to the next); 3) Whether improvement in rhythm persists following offset of stimulation.

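### Aim 2's 90% power for a 7-point movement difference comes from a paired test; the SVS versus SCC comparison with 25 infants per group has about 68%

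*Combined protocol and SAP*

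**What the plan says.** Section 2.4.2 names movement as the primary outcome of Aim 2. It cites pilot data from 26 infants: mean movement 40% of the time with stimulation OFF (SD 10%) and 26% with it ON (SD 9%). The calculation is made "assuming a two-sided paired t-test at alpha=0.05 for the unadjusted treatment effect". The result is given as "we estimate 25 infants per group will give us 90% power to detect a reduction of 7% in movement between the two treatment groups", explained as "a relative reduction of about 20% from 40% in OFF to 33% in ON", with an SD of 10% described as conservative.

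Section 2.4 opens with a general claim: "For all Aims there is sufficient sample size to detect clinically meaningful differences with 90% power".

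Section 2.1.2 describes a 1:1 randomised parallel-group trial. Section 4.1.2 words Aim 2 as "Examine physiological responses to SVS compared to SCC at two stages of withdrawal severity". Section 4.3.3 plans both kinds of contrast: "mixed effects models will be used to examine if SVS, within infants and between SVS and SCC infants". For Aims 1 and 3 the power calculations use an ordinary two-sample t-test; only Aim 2 uses a paired one.

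**The concern.** The sentence takes its test from one contrast and its conclusion from another. A paired t-test suits ON against OFF in the same infant. A reduction between treatment groups, with a number of infants per group, is a comparison of independent infants. With the same SD and the same n per group, the variance of that difference in means is twice the paired variance.

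The SD raises a second question. A paired test needs the SD of the within-infant differences. The 10% in the text equals the pilot SD of movement in the OFF condition, and neither an SD of differences nor an ON/OFF correlation is given.

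SVS versus SCC is the randomised comparison and the one named in the aim. If its power is 68%, a true 7-point effect would be missed about 32% of the time, against the 10% a reader of Section 2.4.2 would expect. A non-significant result could then be taken as stronger evidence of no physiological effect than it is.

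**Working it through.** **Inputs, all from Section 2.4.2.** Difference δ = 7 points; SD σ = 10 points; n = 25 (per group, as stated); two-sided α = 0.05. Power is computed from the noncentral t distribution.

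**1. Reproducing the plan's figure (paired).** Noncentrality = (δ/σ)·√n = 0.7 × 5 = 3.50, with 24 degrees of freedom.
- 25 pairs: power 91.9%. For comparison, 24 pairs give 90.7% and 23 give 89.4%.
- Difference detectable at 90% power with 25 pairs: 6.8 points.

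The stated 90% for 7 points is therefore the paired result, with 10% used as the SD of the differences.

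**2. The comparison the sentence describes (two-sample).** Noncentrality = (δ/σ)·√(n/2) = 0.7 × √12.5 = 2.47, with 48 degrees of freedom.
- 25 per group: power 67.9% (69.7% by the normal approximation).
- Difference detectable at 90% power: 9.36 points, that is, 40% down to about 30.6%.
- Size needed for 7 points at 90% power: 43 per group gives 89.4% and 44 gives 90.1%, so 44.

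**3. Whether another reading of the inputs rescues 90% with 25 per group.**

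| Variant of the two-sample test | Power |
|---|---|
| One-sided | 78.7% |
| SD 9 (pilot ON) | 76.9% |
| SD 9.5 (pooled pilot SDs) | 72.2% |
| Difference of 8 points (exactly 20% of 40%) | 79.1% |

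An SD of about 7.5 would be needed for 90% at 7 points.

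**4. Using both physiology sessions.** Table 3 in Section 3.2 lists two full physiology studies. If each infant's two values are averaged, the SD becomes 10·√((1+r)/2), where r is the between-session correlation. The documents give no value, so r is assumed:

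| r | Power, 7 points, 25 per group |
|---|---|
| 0.3 | 85% |
| 0.5 | 80% |
| 0.7 | 75% |

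Reaching 90% requires r of about 0.1 or less.

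**5. The SD in the paired calculation.** From the pilot SDs, the SD of the differences is √(10² + 9² − 2·10·9·ρ) = √(181 − 180ρ). Setting this to 10 gives ρ = 81/180 = 0.45. The documents do not give ρ, so it is varied:

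| Assumed ON/OFF correlation ρ | SD of difference | Paired power, 25 infants |
|---|---|---|
| 0 | 13.5 | 70% |
| 0.3 | 11.3 | 85% |
| 0.45 | 10.0 | 92% |
| 0.7 | 7.4 | 99% |

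**6. Relative reduction.** 7/40 = 17.5%, which the plan gives as about 20%.

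**The case against.** The strongest reply is that the calculation was always about ON versus OFF within infants. The pilot data, the paired test and the OFF-to-ON gloss all point that way, and Section 4.3.3 plans a within-infant analysis. On that reading the 90% reproduces. This stands as an explanation of where the number came from, but it does not save the text. The words about the two treatment groups would be wrong, and the SVS versus SCC contrast would have no power figure despite the claim covering all Aims.

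A second reply is that the planned analysis is a mixed model with repeated sessions and covariates, so 68% is only an unadjusted benchmark. That is fair, and the true power of the planned model cannot be derived from the documents. If covariates explained 20% to 30% of the variance (an assumption), two-session power would run from about 84% to 95% for r from 0.7 to 0.3. But Section 2.4.2 claims no such gain: it specifies the unadjusted effect and gives no correlation, whereas Sections 2.4.1 and 2.4.3 do.

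Third, the SD may be adequate. A positive ON/OFF correlation is plausible, and above 0.45 the paired power exceeds the stated figure. The point that survives is that 10% must be identified and checked, not that it is wrong.

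Fourth, the consequences are limited. The pilot difference was 40 − 26 = 14 points, for which 25 per group gives 99.8% power in the two-sample test, and Aim 2 is a single-site sub-study. This bears on how serious the error is. It does not make the 7-point statement true. The 17.5% versus about 20% point is minor rounding.

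**Conclusion.** The concern holds. The 90% in Section 2.4.2 is a paired result attached to a comparison of independent groups. For SVS versus SCC with 25 infants per group, an SD of 10% and two-sided α of 0.05, power for 7 points is 67.9%, and the difference detectable at 90% power is about 9.4 points. These figures assume one movement value per infant, 10% as the between-infant SD, no covariate adjustment and no dropout; the plan states no dropout for Aim 2. Averaging two sessions raises power to 75–85% over the assumed correlations of 0.7 to 0.3. The paired 90% is valid for the within-infant contrast only if the SD of the ON/OFF differences is about 10%, which the plan does not establish.

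**What to change.** Keep 25 per group and rewrite Section 2.4.2 with two separate statements:

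- **SVS versus SCC:** two-sample t-test, between-infant SD 10%, 90% power for a 9.4-point difference and 68% for 7 points. State whether the SVS value comes from ON periods or from the whole session, because this determines the effect being compared. If credit is wanted for two sessions or for covariates, state the assumed correlation or variance explained.
- **ON versus OFF within the 25 SVS infants:** paired t-test, 7 points at 90% power, with 10% identified as the SD of the within-infant difference and checked against the 26-infant pilot data.

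Limit the opening claim of Section 2.4 so that it does not promise 90% power for a 7-point SVS versus SCC difference. While editing, change the relative reduction to 17.5%.

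The cost is protocol and SAP wording, plus one check of data the sponsor already holds. No infants are added and conduct does not change. The stated detectable difference becomes less favourable.

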3.2. Projected Timetable

Benchmarks	Year 1	Year 2	Year 3	Year 4	Year 5
Estimated Enrolled Subjects UMass/UPitt (230 total: 100UMass; 130UPitt)	25/22	25/36	25/36	25/36	
Data Safety and Monitoring Board: Bi-annual reports	Х	Х	х	х	х
Monthly Meetings with Research Personnel	Х	Х	Х	Х	Х
Investigator Site Visits	Х	Х	Х	Х	Х
Aim 1 and Aim 2: Newborn In-hospital Studies: Demographic/Medical Histories; Mattress SVS/SSC (daily); Actigraph (daily); 2 full physiology studies (10-15/yr)	х	х	х	х	х
Aim 3: Outcomes Studies Telephone Interviews; Outpatient Outcomes (3 sessions)	Х	Х	Х	х	Х
End of Year Report: Deliver up-to-date data base (demographic, medical, actigraph, outcomes testing); Deliver copy of study logs; Summary Report by site PIs	Х	х	х	х	Х
Investigators Present Preliminary Data at Scientific Conference/s			х	х	х
Data Collection Complete				Newborn Studies	Outcomes Testing
Final data sets delivered to UMass biostatisticians; PIs submit final site reports: study enrollment and attrition for each arm of study; Final Analysis and Writing					х

Table 3. Timeline of Benchmarks.

3.3. Target Population Distribution (e.g, Women, Minorities, etc)

The proposed study requires involvement of human subjects, specifically infants, for the purpose of investigating the therapeutic efficacy of SVS for reducing symptomatology and pathophysiological instabilities associated with neonatal abstinence and drug withdrawal, and for improving neurobehavioral outcomes. We will attempt to recruit subjects who are male or female, and from all ethnic backgrounds. We will not exclude subjects for any reason based on race, sex, religion, ethnic background or national origin. The racial mix of the Worcester, MA and Pittsburgh, PA regional areas are identified in Table 4. We expect to be able to do the same for the proposed study with the caveat that the proportions of minorities will reflect the approximate subpopulation proportions of patients admitted to UMass and UPitt with intrauterine opioid exposure.

Maternal Race	UMass (%)	UPitt (%)
African American	5.3	19.7
Hispanic or Latino	10.5	1.1
Asian	4.7	2.4
Caucasian	78.8	75.2
Native American	0.4	0
Two or More Races	2	1.6

Table 4. Demographic Characteristics of Regional Maternal Population.

4. DATA MANAGEMENT AND STATISTICAL ANALYSIS PLAN

4.1. Data Acquisition and Transmission

4.1.1. Specific Aim 1. Determine the efficacy of SVS as a non-pharmacological therapy complementary to standard clinical care (SCC) for reducing severity and duration of opioid withdrawal in newborns compared to SCC alone - Standard Measurements and Recordings.

1) Medical history. Prenatal exposure (e.g., prescribed maintenance therapy, prescription drugs and substance use during pregnancy including toxicology screens indicating drugs of exposure) and demographic data (gender, race, gestational age, birth weight, birth head circumference, delivery mode, anesthesia at delivery) will be obtained from infant and mother via guestionnaire and medical records to help identify variables that may be associated with withdrawal and outcome measures. Subject's medical records will be reviewed and additional history will be obtained from parent/quardian, including review of child's mother medical records if the child was delivered at UMass. We request protected health information from general medical records and review of statutorily protected records at this institution to: 1) Obtain toxicology reports indicating drugs of exposure and other relevant records pertaining to NAS; 2) Make sure the child meets our inclusion criteria. An example would be to confirm that a child has not been diagnosed with a disorder that may cause cardiorespiratory instability, such as intraventricular-hemorrhage greater than grade 2; 3) Obtain information about factors that may affect responses we observe during stimulation. For example, pregnancy or delivery complications, exposure to drugs in utero, or prescribed medications that may alter breathing and heart rhythms. We request to review both the child's and mother's medical records for information from cardiac studies, nursing and respiratory therapy notes, clinical monitor information, discharge summaries, EEG/EMG studies, laboratory results, operative procedures, conclusive pathologies, clinical problem list, and pulmonary, radiology and rehabilitation information. There will be 1-year follow up on study infants through medical record and telephone interview. Data will be entered by a research investigator via secure password protected computer into REDCap database (REDCap Consortium, Vanderbilt University) – see 4.2 below Data Entry Methods.

2) Chart Review/Bedside Log. NAS severity scores. The infant's clinical-care nurses at each site are routinely trained on the NAS assessment tool (modified

Finnegan Scale)^[63] as part of clinical education; this helps ensure reliability of scores. Nurses score the infants' withdrawal severity ~every 3-4 hrs to assess changes in central, autonomic, vasomotor and gastrointestinal function. Daily NAS scores, weight (gain/loss; trajectory), head circumference, routine feed type (formula or breast milk), pharmacological management (medication, dose normalized for body weight), and birth date and date of hospital will be obtained from medical and/or nursing chart review. A computerized and/or paper log (de-identified, subject id only) will be kept by the infant's bedside to record when the infant is in the crib, and nursing/parent interventions (e.g., feeds, diapering, caregiver cuddling, and placement in motorized swings). This provides some indication of the infant's routine clinical care since investigators cannot be at the bedside 24/7. A separate log kept by investigators will be used to record preprogrammed time onset and offset of SVS (i.e., to verify daily automated SVS coinciding with log indicating when infant is in the crib to receive the intervention). Data will be entered by a research investigator via secure password protected computer into REDCap database.

3) Movement Activity. Movement periods will be assessed via actigraphy, a simple non-invasive measurement using a wireless, lightweight sensor worn around the infant's limb (Respironics[®]). The sensor is ~1.5"x1" and held in place with a soft foam tapeless wrap (Posey[®]). Actigraph sensors applied to the infant's limb will continuously record the frequency of movements throughout the duration of the infant's hospitalization, starting within 24-48 hrs post birth. This will allow measurement of frequency of leg movements (index of irritability, sleep fragmentation, wake and quiescence (index sleep) throughout hospitalization).^[46, 47] Data will be recorded in 1-min epochs to evaluate for movement frequency (index of activity) and quiescence over 12h and 24h intervals and/or during periods when infants are documented in the crib (mattress on or off). Digitized signals will be stored on electronic data base. Data will be analyzed via computerized programs, stored in excel spreadsheets, and entered by a research investigator via secure password protected computer into REDCap database.

4.1.2. Specific Aim 2. Examine physiological responses to SVS compared to SCC at two stages of withdrawal severity – Standard Measurements and Recording.

Changes and relationships among physiological signals will be quantified in a sub-population of study infants at UMass. For each session, physiological signals will be recorded continuously for ~6-8 hrs using proprietary acquisition system. Respiratory inductance plethysmography will be used to measure infant's breathing (Somonstar[®]); infant's abdominal muscle movement will provide detection of interbreath intervals (index of respiratory stability) and respiratory rate. Electrodes over the skin surface of the chest will be used to record electrocardiographic activity (ECG; Embla[®]) to allow for detection of cardiac R-R intervals (index of interbeat variance and heart rate). A probe attached to the infant's foot will measure arterial-blood oxygen concentration (Masimo[®]). Quality of the plethysmographic activity characterized in the pulse signal will also allow for identification of movement period duration. Movement frequency will be assessed with actigraphy using a wireless sensor worn around the infant's limb (Respironics[®]).

the infant's armpit or back (Physitemp[®]). Environmental changes in sound intensity and light level will be measured with meters placed in the crib near the infant's head (Extech[®]). Overt behavioral data will be recorded using sound-video camera with a wide-angled lens.

Physiological data will be digitally recorded (~50-1kHz samples per channel) using an acquisition system that directly obtains signals from the NICU bedside monitor (Philips[®]; Wyss Institute, Harvard University) or via an independent system (Embla[®]). These systems enable fully synchronized recordings of physiological signals, audiometry, photometry and digital video images. Comments regarding routine nursing assessments and other relevant information (e.g. feeding, pharmacological dosing) will be typed and time stamped along with the physiological data stream. Acitgraph activity will be digitally recorded independent of the full-acquisition system. All signals, video images and germane data (e.g., medical histories of infant and mother, NAS severity assessments) will be stored on electronic data base. Investigators will also manually record relevant study information (timing and mode of experimental conditions, nursing assessments, feeds, medications etc) stored in the electronic data base.

Data is analyzed via proprietary software and via advanced computational models of analysis developed for this study. Final outputs will be stored on password protected computers in excel data bases and will be entered by a research investigator via secure password protected computer into REDCap database.

4.1.3. Specific Aim 3. Compare neurobehavioral outcomes in the first year of life between infants who received SVS and those who received SCC – Standard Measurements and Recordings.

1) Follow-up Chart Review and Telephone Interview. For a period of up to 14 months post hospital discharge we will review hospital medical records for inpatient and outpatient visits (if the infant is treated at UMass or UPitt) for information related to outcomes for neonatal drug exposure. We will also follow-up for 14 months post-hospital discharge with phone-call questionnaires (approx. every other month) to help identify outcomes associated with infants requiring prolonged pharmacotherapy and those discharged without medication, and to determine if there are differences in outcomes in infants treated with SVS vs SSC. Data will be entered by a research investigator via secure password protected computer into REDCap database.

2)Anthropomorphic Examination. Infant weight, height, and head circumference are measured in the delivery room and recorded in medical record throughout hospitalization. Data will be entered by a research investigator via secure password protected computer into REDCap database.

3) Neurobehavioral Assessments. Outpatient assessments will be conducted at 1 month, 6 months and 12 months (see Table 2). Data will be entered by a research investigator via secure password protected computer into REDCap database.

